*The ILD diagnosis date will be defined as the first date of a claim with diagnosis for fibrosing ILD during the identification period. Patients will be followed from the fibrosing ILD diagnosis date until the earlier of disenrollment from the health plan, death, or end of the study period. Figure is not to scale and is for illustrative purposes only.

Figure 2. Observation and Identification Periods: Aim 2

*The fibrosing ILD diagnosis date will be before the index date and may be before or during the pre-index baseline period.

†The index date will be defined as the first date of a claim with oxygen therapy (oxygen therapy cohort), or a date that is eligible for index and is similar to the matched case's index date (no oxygen therapy cohort).

Patients will be followed from the index date until the earlier of disenrollment from the health plan, death, or end of the study period.

Figure is not to scale and is for illustrative purposes only.

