7.2 SETTING

7.2.1 Secondary data source selection

The study will use administrative claims and EHR data from Optum's Market Clarity Integrated Claims + Clinical database.

7.2.2 Study population: Aim 1

The analysis for Aim 1 will include patients newly diagnosed with fibrosing ILD during the patient identification period. Patients must meet the following selection criteria to be included in the study:

Inclusion Criteria

- ≥ 2 fibrosing ILD diagnoses in any position on different dates of service, within 365 days of each other, and in the same continuous enrollment period during the patient identification period. The ***fibrosing ILD diagnosis date*** will be defined as the date of the first fibrosing ILD diagnosis. The two fibrosing ILD diagnosis codes can be one of the following combinations:
 - 2 fibrosis codes
 - 1 fibrosis code & 1 ILD code that requires fibrosis code
- ≥ 18 years of age as of the fibrosing ILD diagnosis date
- Continuous enrollment with medical and pharmacy coverage for 12 months prior to the fibrosing ILD diagnosis date (***pre-ILD baseline period***)

Exclusion Criteria

- Fibrosing ILD diagnosis in the 12-month pre-ILD baseline period
- Unknown gender or geographic region

Cohort Assignment

Patients meeting initial selection criteria for Aim 1 will be assigned to cohorts based on known cause of fibrosis:

- **IPF**— ≥ 2 medical claims with diagnosis for IPF in any position during the study period
- **Non-IPF ILD**— < 2 medical claims with diagnosis for IPF during the study period

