7.3 VARIABLES

Variables related to the study period will be defined as follows:

Aim 1

- **Fibrosing ILD diagnosis date**—The first ILD diagnosis date for patients with ≥ 2 fibrosing ILD diagnoses on different dates and within 365 days. The fibrosing ILD diagnosis date is the first day of follow-up observation time for Aim 1.
- **Pre-ILD baseline period**—The 12-month period prior to the fibrosing ILD diagnosis date.
- **Aim 1 follow-up period**—The variable period starting on the fibrosing ILD diagnosis date and continuing until the earliest of the following: disenrollment from the health plan, death, or end of the study period. The Aim 1 follow-up period will be used to assess Aim 1 outcomes.
 - **All-cause mortality**—Death will be used as a censoring event and is further defined in Section 7.3.3.1.

Aim 2

- **Index date**—For the oxygen therapy cohort, the first date following the fibrosing ILD diagnosis date with a claim with diagnosis for oxygen therapy; for the no oxygen therapy cohort, a date within the same continuous enrollment period as the fibrosing ILD diagnosis date that is similar to the matched oxygen therapy patient in time from fibrosing ILD to index date. The index date is the first day of follow-up observation time for Aim 2 and Further Aim.
- **Pre-index baseline period**—The 12-month period prior to the index date.
- **Aim 2 follow-up period**—The variable period starting on the index date until the earliest of the following: disenrollment from the health plan, death, or the end of the study period. Matched pairs will be given the same duration of follow-up. The Aim 2 follow-up period will be used to assess Aim 2 and Further Aim outcomes.
 - **All-cause mortality**—Death will be used as a censoring event and is further defined in Section 7.3.3.1.

An overview of the analytic study variables and the study periods for which each analytic variable will be reported is provided in Table 1. Additional variable information is provided in Sections 7.3.1 to 7.3.4.

Table 1. Analytic Variables by Data Source and Time Period

Characteristic	Data source		Aim 1 time period		Aim 2 time period	
	Claims*	EHR	Pre-ILD baseline	Follow-up	Pre-index baseline	Follow-up
Aim 1 outcomes						
Oxygen therapy (time to initiation, sustained oxygen therapy use)		X		X	X	
Aim 2 outcomes						
Disease progression	X	X				X
All-cause mortality	X					X
Hypoxemia	X	X	X		X	X
Acute exacerbations	X	X				X
Patient characteristics†						
Index year	X		X		X	

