7.3.3 Aim 2 Outcomes

7.3.3.1 Primary Outcomes

All primary outcomes will be measured in the Aim 2 and Further Aim follow-up period, unless specified otherwise.

- **Time to disease progression**—Pulmonary function test (PFT) results will be captured as available in the database in the pre-ILD baseline, pre-index baseline, and Aim 2 follow-up periods among the subset of patients who have EHR data during the same

time of ILD diagnosis and oxygen therapy. All valid result values will be captured. Values closest to the fibrosing ILD diagnosis date will be reported for the pre-ILD baseline period; values closest to the index date will be reported for the pre-index baseline period; the latest values prior to the end of follow-up will be reported for the Aim 2 follow-up period. PFT tests may potentially include forced expiratory volume in 1 second (FEV₁), forced vital capacity (FVC), FEV₁/FVC ratio, lung volumes, and diffusing capacity for carbon monoxide (DLCO), as available.

Among patients or matched pairs with FVC results in the pre-index and follow-up periods, disease progression will be defined as a 10% relative change between the pre-index value and the follow-up value. Time to disease progression will be reported. Additionally, time in days from pre-index FVC result to the index date and from index date to follow-up FVC result will be reported.

- **Time to all-cause mortality**—We will assign the date of death as the 15th day in the month of death. Time to all-cause mortality will be calculated as time between index date and mortality date.

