7.3.3.2 Secondary Outcomes

- **Hypoxemia**—Sample size permitting, hypoxemia (i.e., oxygen saturation [SpO₂] <90%) will be captured as available in the database using specific ICD-10-CM codes or EHR data among the subset of patients with both claims and EHR in the Market Clarity database. Time to hypoxemia will be reported as time between index date and first evidence of hypoxemia.
- **Respiratory deterioration/Acute exacerbations**—An acute exacerbation of fibrosing ILD has been defined clinically as an unexplained worsening or development of dyspnea within 30 days in combination with a high-resolution CT indicating interstitial pneumonia, and excluding pulmonary infection, left heart failure, pulmonary embolism or other identifiable causes of acute lung injury.⁹ Based on these clinical criteria, acute exacerbations will be defined as follows:
 - ≥1 claim with procedure code for CT scan, and
 - Evidence of dyspnea, as defined by ICD-10-CM codes or EHR data in the integrated database, within 30 days prior to date of CT scan, and
 - No claims with diagnosis for pulmonary infection, left heart failure, pulmonary embolism, or other identifiable causes of acute lung injury within 30 days prior to date of CT scan.

The time to first exacerbation and population annualized counts of exacerbations (sum of all exacerbations for all individuals / sum of follow-up time [person years] for all individuals) will be described. Exacerbations occurring within 14 days of each other will be considered a single exacerbation episode. The start date of the exacerbation episode will be the service date of the first event (i.e., dyspnea or CT scan). The end date of the exacerbation episode will be defined as the last observed exacerbation event date (or discharge date if event occurs during an inpatient stay) + 14 days. Exacerbation episodes that include an inpatient stay will also be reported separately as exacerbations involving a hospitalization.

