Commercial and Medicare Advantage health plan members with ≥ 1 medical claim or EHR diagnosis for fibrosing interstitial lung disease (ILD) during 01 JAN 2016 and 31 MAY 2022 (study period). First diagnosis is index date.	1,179,017
Patients with at least one evidence for oxygen therapy anytime during the post-index period (12 months)	214,725
Patients aged ≥ 18 years as of the index date	212,466
Patients with at least 6 months of pre-index continuous enrollment and EHR clinical activity	80,151
Patients with at least 6 months of post-index continuous enrollment and EHR clinical activity	34,299

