7.8 LIMITATIONS OF THE RESEARCH METHODS

This study should be considered in the context of its limitations. First, identification of patients with newly diagnosed fibrosing ILD will rely on application of a claims-based algorithm. Presence of a diagnosis code does not necessarily indicate presence of disease; however, to limit misidentification of ILD patients, a confirmatory diagnosis will be required. Further, patients without ILD diagnosis in the 12-month baseline will be considered newly diagnosed. However, it is possible that patients with prevalent ILD who have not sought frequent care for their condition may be misclassified as newly diagnosed ILD patients.

Second, this study will utilize both claims and EHR data available in Optum's Market Clarity Integrated Claims + Clinical database to capture ILD symptoms, pulmonary function testing results, and hypoxemia. EHR data will be available for only a subset of the identified population; for remaining patients, these values will rely on information available in claims. Further, the analysis will rely on the availability of valid values (e.g., laboratory results) in the EHR data.

Third, all ILD patients included in this study were enrolled in a health plan (i.e., commercial, Medicare, or Medicaid) during the study period; thus, findings from this study may not be applicable to uninsured populations and patients with health plans not represented in the database.

Fourth, this study will minimize bias by utilizing propensity score matching on baseline variables (oxygen therapy versus no oxygen therapy cohorts) to examine outcomes of interest. Employing matching will enable a comparison of outcomes among patients who were similar on pre-ILD baseline characteristics. However, residual and/or unobserved confounding cannot be ruled out.

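### Aim 2 outcomes that draw on the EHR are followed over plan-enrollment time, with no visible EHR-activity requirement, so detection can differ between the oxygen and no-oxygen cohorts

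*Combined protocol and SAP*

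**What the plan says.** **Follow-up.** Section 7.3 defines the Aim 2 follow-up period as "starting on the index date until the earliest of the following: disenrollment from the health plan, death, or the end of the study period", and uses it for all Aim 2 outcomes. The note to Figure 2 in section 7.1 repeats it: "Patients will be followed from the index date until the earlier of disenrollment from the health plan, death, or end of the study period". Section 7.3 adds: "Matched pairs will be given the same duration of follow-up".

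**Eligibility.** Section 7.2.2 requires "Continuous enrollment with medical and pharmacy coverage for 12 months prior to the fibrosing ILD diagnosis date". Neither it nor section 7.2.3 asks for EHR activity.

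**FVC progression (7.3.3.1).** PFT results are taken in patients with EHR data at the "time of ILD diagnosis and oxygen therapy. All valid result values will be captured". Progression is then defined only for patients or pairs with an FVC both before index and during follow-up.

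**Hypoxemia (7.3.3.2).** It is captured "using specific ICD-10-CM codes or EHR data among the subset of patients with both claims and EHR in the Market Clarity database".

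**Exacerbations (7.3.3.2).** CT comes from claims, and dyspnea from ICD-10-CM codes or the EHR. The annualized count divides by all follow-up person-years.

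**Limitations (7.8).** EHR data exist for only a subset, and "for remaining patients, these values will rely on information available in claims". Pulmonary function and hypoxemia are among the values meant.

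**Feasibility (7.5, Table 3).** The last row counts "Patients with at least 6 months of post-index continuous enrollment and EHR clinical activity".

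**The concern.** An enrolled patient can stop being seen in the EHR network. From then on an SpO2 reading or an EHR-only note of dyspnea can no longer be found, although the patient still contributes time at risk. If one cohort keeps EHR contact longer than the other, the same true event rate produces different observed rates.

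Two wording problems make this worse. The EHR condition for PFT results is tied to the time of oxygen therapy, and comparators have no such date, only an assigned index date. And sections 7.3.3.2 and 7.8 give different answers on whether a patient without EHR data belongs in the hypoxemia analysis. Under the second, patients observed with different sensitivity are pooled in one estimate.

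Disease progression is a primary outcome in section 7.3.3.1. The abstract also lists hypoxemia and exacerbations as primary, while section 7.3.3.2 calls them secondary.

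**Working it through.** The plan states no event rates, power or EHR coverage by cohort, so there is no planned figure to reproduce. The check has three parts.

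**1. What enrolled time without EHR contact does to each outcome**

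- *Hypoxemia:* ICD-10-CM codes are still seen and SpO2 readings are not. Time stays at risk and detection falls.
- *Exacerbations:* CT claims and coded dyspnea are still seen and EHR-only dyspnea is not. Person-years stay in the denominator and detection falls.
- *FVC progression, no follow-up test:* the patient is excluded under 7.3.3.1. This is selection on having a later test.
- *FVC progression, an early stable test and no later EHR contact:* the patient qualifies. No FVC-specific censoring date is visible, so under the 7.3 rule the patient stays at risk, progression-free, until plan exit, death or study end.
- *Mortality:* Table 1 marks claims only, so EHR contact plays no part.

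**2. What Table 3 can show**

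Requiring 6 months of post-index enrollment and EHR activity takes 80,151 to 34,299. The loss is 80,151 − 34,299 = 45,852, and 45,852 / 80,151 = 57.2%. All of these patients already had evidence of oxygen therapy, the index there is the first ILD diagnosis, and the step combines enrollment with EHR activity. The figure shows that coverage may be incomplete. It does not measure EHR loss among enrolled patients and says nothing about comparators.

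**3. How differential contact would act (illustration; all inputs assumed)**

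Let f be the share of enrolled time with EHR contact and c the share of events also coded in claims. Events are taken as rare, detection as complete during contact, and the true rate ratio as 1.

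Capture = f + (1 − f) × c; apparent ratio = capture (oxygen) / capture (no oxygen).

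| c | f = 0.8 oxygen, 0.6 no oxygen | f = 0.6 oxygen, 0.8 no oxygen |
|---|---|---|
| 0 | 0.80 / 0.60 = 1.33 | 0.60 / 0.80 = 0.75 |
| 0.25 | 0.85 / 0.70 = 1.21 | 0.70 / 0.85 = 0.82 |
| 0.5 | 0.90 / 0.80 = 1.13 | 0.80 / 0.90 = 0.89 |
| 0.75 | 0.95 / 0.90 = 1.06 | 0.90 / 0.95 = 0.95 |
| 1 | 1.00 | 1.00 |

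Equal f in both cohorts gives 1.00 at any c. The row c = 0 is an extreme, because the plan does use claims codes. In a codes-only analysis capture is c in both cohorts, so the ratio is c / c = 1.00 if coding is equally complete in each. If follow-up ends with EHR activity, f = 1 in both and the ratio is again 1.00, provided loss of contact is unrelated to risk.

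**The case against.** The case against has real force.

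- **FVC.** A reader might infer that patients who leave the EHR are counted as progression-free. For those with no follow-up FVC this is wrong, since section 7.3.3.1 excludes them. Only the patient with an early stable test remains a problem.
- **Hypoxemia and dyspnea.** A reader might infer that such patients are unobservable. They are not: codes still capture events, and Table 1 marks both sources. Under-ascertained is the right word.
- **Direction.** A reader might infer that oxygen will be made to look harmful. That needs comparators to have less EHR contact, which the documents do not say. The reverse gives the opposite bias.
- **Table 3.** A reader might take the 57.2% as EHR dropout, or think a study rule was dropped. The count mixes causes, covers oxygen patients only, and is described in section 7.5 as informational.
- **The oxygen-therapy wording.** The assigned index date is the evident counterpart for comparators, so this is loose drafting and easily repaired.
- **Unavailable text.** Section 7.2.3 refers to section 7.6.2.2, which is not in the public text. Outcome-specific censoring may stand there, and section 7.2.3 allows the Aim 2 criteria to be revised.
- **Remedy.** EHR contact is driven by illness. A hard stop at last contact keeps events but drops later event-free time, which inflates rates most where contact is sparse.

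All of this narrows the point without removing it. Equal follow-up within pairs does not help, because EHR contact can differ within equal enrolled time. The limitations section admits partial EHR coverage but not that contact can lapse during follow-up. The conflict between sections 7.3.3.2 and 7.8 is in the visible text.

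**Conclusion.** The concern holds in a limited form, and the sponsor should act on it. On the visible definitions, EHR-dependent Aim 2 outcomes are assessed over enrollment time, with no EHR-activity requirement at entry and no EHR-based end of observation. Hypoxemia and exacerbations are under-ascertained in enrolled time without EHR contact, and this biases the comparison if contact differs between cohorts. For FVC progression the defect is the missing censoring date after the last test. The EHR condition in 7.3.3.1 does not fit comparators as worded, and 7.3.3.2 and 7.8 must be reconciled.

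The size and direction cannot be obtained from the documents. The range 0.75 to 1.33 rests on assumed contact shares of 0.8 and 0.6 and shrinks towards 1.00 as claims capture rises. Nothing here shows that the bias is present, only that the visible text does not guard against it. Mortality is unaffected.

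**What to change.** 1. In section 7.3.3.1, tie the EHR condition to the index date instead of oxygen therapy. For EHR-dependent outcomes, require EHR activity in the pre-index baseline in both cohorts.
2. Run hypoxemia, and the dyspnea part of exacerbations, as a codes-only analysis in all patients and separately as a codes-plus-EHR analysis in the EHR-active subset. Do not mix the two in one estimate. Reconcile sections 7.3.3.2 and 7.8 accordingly.
3. Censor patients without FVC progression at their last FVC.
4. As a sensitivity analysis for the codes-plus-EHR outcomes, end follow-up when EHR activity ends, for example at last contact plus a fixed grace period. Report EHR-observed time by cohort, so that readers can judge whether contact differs.
5. Leave the follow-up rule for mortality as it is.

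If section 7.6.2 already contains any of this, a cross-reference from section 7.3 is enough for that part.

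The cost is wording plus an EHR-activity flag and end date per patient. The EHR analyses will have a smaller sample, and follow-up will be shorter for FVC and in the sensitivity analysis. EHR contact may itself be informative, which is why the stop at the end of EHR activity belongs in a sensitivity analysis.

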date (i.e., similar to the matched oxygen therapy patient in time from the fibrosing ILD diagnosis date to the index date, and during the same continuous enrollment period as the fibrosing ILD diagnosis date).

NOTE: Following review of results from Aim 1, the study team will determine whether continuous enrollment criteria for Aim 2 and Further Aim requires revision.

Variables:	
Aim 1
 
Outcomes: time to initiation of oxygen therapy; time to sustained oxygen therapy use; sustained oxygen therapy use within the first 12 months of follow-up
 
Baseline covariates: demographic characteristics (age, sex, race/ethnicity, geographic region, insurance type, index year), clinical characteristics (underlying ILD type; respiratory diseases; other clinical characteristics; Quan-Charlson comorbidity score; Agency for Health Research and Quality [AHRQ] comorbid conditions; smoking; pulmonary rehabilitation) healthcare utilization characteristics (provider specialty; medication use; all-cause HCRU; all-cause health care costs)
 
Stratification: IPF vs non-IPF ILD
 
Aim 2 [REDACTED]
 
Exposure: oxygen therapy vs no oxygen therapy
 
Primary Outcomes: Time to disease progression; time to all-cause mortality; time to hypoxemia, time to acute exacerbations, counts of acute exacerbations
 
[REDACTED]
 
Baseline covariates: demographic characteristics (index year, age, sex, race/ethnicity, geographic region, insurance type), clinical characteristics (underlying ILD type; respiratory diseases; other clinical characteristics; Quan-Charlson comorbidity score; AHRQ comorbid conditions; smoking; pulmonary rehabilitation) healthcare utilization characteristics (provider specialty; medication use; all-cause HCRU; all-cause health care costs)

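### Dating deaths to the 15th of the month gives some patients negative survival times with no stated floor; separately, the public text does not say how equal pair follow-up is set or whether it should apply to mortality.

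*Combined protocol and SAP*

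**What the plan says.** All-cause mortality is a primary Aim 2 outcome (Abstract, Variables; Section 7.3.3.1). Two rules bear on it.

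- **Death date.** Section 7.3.3.1: "We will assign the date of death as the 15th day in the month of death", followed by "Time to all-cause mortality will be calculated as time between index date and mortality date". The index date is an exact date (Section 7.3). No floor or exception is given in the public text.
- **Follow-up.** Section 7.3 ends each patient's Aim 2 follow-up at the earliest of disenrollment, death or study end, then adds: "Matched pairs will be given the same duration of follow-up". It uses that period for Aim 2 outcomes. Section 7.3.3.1 confirms: "All primary outcomes will be measured in the Aim 2 and Further Aim follow-up period, unless specified otherwise". Nothing else is specified for mortality.

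Section 7.2.3 refers matching to Section 7.6.2.2, which is not in the public file. The exacerbation measure in Section 7.3.3.2 is already a rate: "sum of all exacerbations for all individuals / sum of follow-up time [person years] for all individuals". FVC progression uses the last value in the window: "the latest values prior to the end of follow-up will be reported for the Aim 2 follow-up period".

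**The concern.** **Death date.** The rule moves a death late in a month back to the 15th, while the index date stays put. Index on 20 March and death on 28 March gives 15 March minus 20 March, or −5 days. Index on the 15th with death later that month gives zero. Survival procedures may drop or mishandle such records. They are all deaths soon after index, so an ad hoc repair would act on early mortality in a primary outcome.

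**Equal duration.** A patient who has died or left the plan cannot be followed for longer, so durations can be equalised only by shortening the partner's. Deaths in the time removed are in the database but would not count in a marginal (unstratified) analysis. Hypoxemia and exacerbation follow-up would be shortened in the same way. Survival and rate methods do not need equal windows.

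**Working it through.** The documents give no death or disenrollment rate and no target event number, so there is no planned figure to reproduce. All rates below are assumptions.

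**Death date**

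1. In a 365-day year, count for each index date after the 15th the later days left in that month. A 31-day month gives 15+14+…+0 = 120, a 30-day month 105, and February 78. Total: 7×120 + 4×105 + 78 = 1,338. The mean is 1,338/365 = 3.67 days at risk of a negative time per patient. Counting death on the index day itself adds 185/365 = 0.51, giving 4.17.
2. Share of deaths within 30 days of index, spread evenly: 3.67/30 = 12.2% (lags 1–30 days) or 4.17/31 = 13.5% (lags 0–30). A simulation at constant hazard gave about 14%. A further 1.7% get exactly zero (lags 1–30).
3. Share of patients at constant hazard: 0.15×3.67/365 = 0.15% to 0.30×4.17/365 = 0.34%.
4. Share of first-year deaths: 0.15/13.9 = 1.1% to 0.34/25.9 = 1.3%, where 13.9% and 25.9% are 1−exp(−0.15) and 1−exp(−0.30). At 0.40 per year it reaches 1.4%. If the hazard is tripled for the first 30 days it is 2.8–3.4%.

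**Equal duration**

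Assume exponential death at rate d = 0.15–0.30 and disenrollment at rate c = 0.15–0.5 per year, the same in both members. Study-end time is uniform over 0 to T = 5.75 years (01 October 2016 to 30 June 2022). Let

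- I(a) = 1/a − (1−exp(−aT))/(a²T), for one study-end time or one shared by the pair;
- J(a) = 1/a − 2/(a²T) + 2(1−exp(−aT))/(a³T²), for the earlier of two independent study-end times.

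The probability that a patient's death is observed is d·I(d+c) with own follow-up. It has argument d+2c if the pair is cut at either member's disenrollment or study end, and 2d+2c if also cut at the partner's death. I applies with shared dates, J with independent dates. The ends of each range are:

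| Cut | Dates in pair | d, c | Own | After cut | Loss |
|---|---|---|---|---|---|
| Disenrollment or study end | shared | 0.30, 0.15 | 0.428 | 0.360 | 16% |
| Disenrollment or study end | independent | 0.15, 0.5 | 0.170 | 0.097 | 43% |
| Also partner's death | shared | 0.15, 0.15 | 0.262 | 0.180 | 31% |
| Also partner's death | independent | 0.30, 0.5 | 0.294 | 0.151 | 49% |

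The public text aligns controls on time since diagnosis, and index year is among the listed covariates ("demographic characteristics (index year, age, sex, race/ethnicity, geographic region, insurance type"). If partners share index year, the loss with the partner's-death cut is 34–44%. With that cut and wider rates (d 0.05–0.5, c 0.05–0.8) it is 15–49%. With fixed follow-up (d 0.05–0.5, c 0–0.5) it is only 1–18% at six months and 2–29% at one year.

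**Consequence**

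- The standard error of the log hazard ratio grows by 1/√(1−loss): 1.09 at 16%, 1.20 at 31%, 1.32 at 43%, 1.40 at 49%.
- With an assumed 20% observed deaths per arm and n pairs, the 95% margin on the hazard ratio is exp(1.96·√(2/(0.2·n·(1−loss)))). For losses of 16–49% it goes from 1.22 to 1.24–1.32 at 1,000 pairs, from 1.09 to 1.10–1.13 at 5,000, and from 1.04 to 1.04–1.05 at 30,000.
- Simulated Cox models on 20,000 pairs: cutting at the first exit reduced deaths from 9,807 to 6,661. The unstratified standard error rose from 0.0211 to 0.0260 (hazard ratio 2.03 and 1.99). The pair-stratified estimate and its standard error (0.0260) were identical with and without the cut.
- With death rates of 0.25 and 0.15 per year and independent partners, the ratio of retained deaths was 1.67–1.68 against a true 1.67.
- Kaplan-Meier mortality falls only if partners share risk. With gamma frailty variance 1 and within-pair correlation 0.25, two-year mortality moved from 33.2% to 32.5–32.7% (oxygen) and from 23.1% to 22.2–22.3% (control).

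**The case against.** The strongest objection is that the equal-duration point rests on text that is not public. Section 7.6.2 may define the rule, limit it to some outcomes, or specify a pair-stratified model. That stands: its absence from the public file is no omission by the sponsor, and the request must be conditional.

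A reader might infer that a third to a half of deaths will be lost. The documents do not support that. A cut at the partner's death is only one reading, a cut at disenrollment or study end loses less, and every percentage depends on assumed rates and follow-up.

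A reader might also infer a biased hazard ratio. Shortening pairs does not by itself cause that. If partners share unmeasured risk, the cut moves an unstratified estimate towards the pair-stratified one, which changes the quantity estimated.

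Nor does Section 7.3 contradict itself by calling death a censoring event. Death can end follow-up and still be the event in the mortality analysis, although the wording could say so.

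Two further objections have weight. Controls are patients who had not yet started oxygen (Section 7.1), so following them longer can add time after they start; equal windows limit this. And the date rule touches few patients and might be handled in programming specifications. It is nevertheless a stated rule that yields impossible times, and it costs almost nothing to correct.

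**Conclusion.** The date rule needs correcting as written. That negative times can occur follows from the text alone; how often depends on assumed hazards and index dates spread evenly over the calendar. The effect is small overall and concentrated in the first month.

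The equal-duration point holds as a conditional request to clarify and, where needed, to narrow the rule. An unstratified mortality analysis would lose observable deaths for no statistical gain. The loss is about 16–43% or 31–49% depending on the cut, under the rates above, and smaller with lower rates or shorter follow-up. The price is precision: negligible near the feasibility count of 34,299 oxygen patients (Table 3, different criteria, final number unknown), and more noticeable in subsets of about 1,000 pairs.

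**What to change.** 1. In both cohorts, set the assigned death date to the later of the 15th and index date + 1 day. Add an end-of-month death date as a sensitivity analysis.
2. State how pair durations are equalised and to which outcomes this applies, and that death is the event in the mortality analysis.
3. Unless Section 7.6.2 already does so, follow each patient to their own disenrollment, death or study end for time to death, time to first hypoxemia, time to first exacerbation and exacerbation rates, with pair-clustered (robust) variance.
4. Keep equal pair follow-up for HCRU and cost summaries and for FVC progression based on the last value, because these depend on window length.
5. Report how often, and when, controls start oxygen during their own follow-up, and keep the equal-duration mortality analysis as a sensitivity analysis.

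The cost is protocol and SAP wording and minor programming, with no new data. The downsides are two follow-up definitions to label in the tables, and longer control follow-up that may include time on oxygen, which item 5 makes visible.
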